6.3. Dose De-Escalation Schema for Tolerability Phase

If the suggested lidocaine dose is tolerable in four consecutive sessions of mFOLFOX6 in six or more of the eight patients in the tolerability phase, we will initiate the randomized efficacy pilot study with the suggested dose. Tolerability will be defined as lack of dose-limiting toxicities (DLT) associated with lidocaine treatment (defined in Section 6.4.2), and no signs of unanticipated disease progression as evidenced by the routine PET/CT scan (as clinically indicated) performed after 4th cycle of mFOLFOX6. After four cycles of 1st line treatment with mFOLFOX6, approximately 80% of patients respond or remain progression-free [44]. If three or more patients in the tolerability study develop DLT or unanticipated disease progression after 4 consecutive cycles of oxaliplatin, dose de-escalation will occur based on the following table.

Lidocaine	Initial bolus dose over 10 min	Infusion rate	Total dose
dose level	(based on IBW)	(over 120 min)	
#1	1.0 mg/kg	0.04 mg/kg/min	5.8 mg/kg IBW
#2	0.8 mg/kg	0.03 mg/kg/min	4.4 mg/kg IBW
#3	0.6 mg/kg	0.02 mg/kg/min	3.0 mg/kg IBW
#4	0.4 mg/kg	0.01 mg/kg/min	1.6 mg/kg IBW

IBW= Ideal Body Weight

6.4. Definition of Maximum Tolerated Dose, Dose De-Escalation Criteria, and Toxicity and DLT Evaluations

6.4.1. Definition of Maximum Tolerated Dose

Dose escalation will not be performed in this study; therefore no formal maximum tolerated dose (MTD) will be defined. MTD for this study purposes will be defined as either the initial dose regimen (dose level #1, table above), or as the dose level immediately below the dose level at which >2 patients of a cohort experience dose-limiting toxicity over 4 consecutive sessions of mFOLFOX6. Dose de-escalations will proceed if needed until the MTD has been ascertained.

6.4.2. Dose-Limiting Toxicities

Dose limiting criteria for lidocaine include the appearance of any of the following effects during the study drug infusion or up to 60 minutes thereafter:

- Any of the following cardiac arrhythmias:
- Atrial Fibrillation Grade 3+
- Atrial flutter, Grade 3+
- Asystole, any
- Cardiac arrest
- Atrioventricular (AV) block, Grade 3+
- Paroxysmal atrial tachycardia, Grade 2+
- Sinus bradycardia, Grade 2+
- Sinus tachycardia, Grade 3+
- Ventricular arrhythmia, Grade 2+
- Ventricular fibrillation, any
- Seizure, any
- Dizziness, Grade 3+
- Somnolence, Grade 3+
- Syncope, any
- Blurred vision, Grade 3
- Occurrence of any other Grade 3 or higher adverse effect thought to be at least probably associated with lidocaine treatment.

In addition, a dose-limiting toxicity will be an evidence of unanticipated disease progression based on a routinely performed CT, PET or MRI scan (as indicated, and interpreted by the treating physician) at 8 weeks after oxaliplatin initiation – i.e. 4 cycles of treatment. This may indicate that the study drug negatively affects the efficacy of mFOLFOX6 chemotherapy.

6.4.3. Dose De-Escalation Criteria

Dose de-escalations will proceed as follows after the occurrence of dose-limiting toxicity (DLT):

Number of Patients with DLT at a Given Dose Level	Escalation Decision Rule
Less than three of 8 subjects	Proceed to the randomized phase of the study.
Three or more subjects	De-escalate the dose by entering 8 patients at the next lowest dose level.

6.5. Toxicity and DLT Evaluations

All patients who receive any study treatment are evaluable for toxicity. Patients are evaluated from first receiving any study treatment until 60 minutes following end of each infusion of lidocaine. There are no concerns with concentration-independent toxicity of lidocaine with intermittent administration such as in this study.

DLT, also defined as drug dose that interferes with oxaliplatin efficacy or otherwise unanticipated disease progression, will be assessed by a CT, PET or MRI scan at 8-weeks, or as clinically indicated .

A patient is evaluable for DLT assessment only if enrolled in the dose-finding portion of the study.

6.6. Randomized Phase

In the randomized phase, 30 colorectal cancer patients will be randomized to infusion of intravenous lidocaine or identical placebo (D5W-Dextrose 5% in water), per regimen established in the dose-finding phase. The blinded infusions will be co-administered with oxaliplatin via Y-site [45] for all cycles of mFOLFOX6 protocol (approximately every 14 days). The patients are initially planned to receive the study drug for 8 of the 12 cycles of mFOLFOX6 treatment; if the treating clinician decides to reduce the number of treatment cycles to less than 8, the number of study interventions will be reduced accordingly.

6.7. Blood for Determining Lidocaine Concentration

Blood samples (4mL tubes) for determining lidocaine concentration will be obtained at baseline and 15, 45, 60, 90, 130, and 180 minutes after initiation of infusion baseline. The samples will be put on ice, centrifuged for 10 min at 3000 rpm, plasma will be separated and transferred to 1.5mL vials and stored at -80°C until analysis by HPLC-MS.

Beginning with the 3rd study visit that included study drug administration, only a single 4-mL blood sample for lidocaine plasma concentration will be obtained at 130 minutes after study drug initiation.

6.8. Concomitant Medications and Supportive Care

The patients will continue their chronic medications; including chronic pain medications, provided the dose have been stable for at least 2 weeks. If any of these medications are discontinued during the study, the changes will be recorded. PRN analgesics will not be limited, but their consumption will be carefully recorded. Addition of new medications for treating painful neuropathy (i.e. gabapentin, pregabalin, duloxetine, venlafaxine, tricyclic antidepressants, opioids) will not be allowed during the study. Patients will be withdrawn from the study if the peripheral neuropathy is severe enough to require pharmacological treatment.

Participation in the study will not be allowed if participants are treated with any of the following medications, which may result in serious drug-drug interaction with lidocaine:

- Saquinavir, Lopinavir, Amprenavir, Atazanavir, Delavirdine
- Mexiletine
- Phenytoin, Carbamazepine, Oxcarbazepine, Lamotrigine

- Amiodarone
- Dronedarone
- Dihydroergotamine
- Cimetidine

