6.10. Duration of Therapy

If at any time the constraints of this protocol are considered to be detrimental to the patient's health and/or the patient no longer wishes to continue protocol therapy, the protocol therapy should be discontinued and the reason(s) for discontinuation documented in the case report forms.

In the absence of treatment delays due to adverse events, treatment will continue for up to 6 cycles in the tolerability phase and 8 cycles in the randomized phase of mFOLFOX6 or until one of the following criteria applies:

- Documented and confirmed disease progression
- Death
- Adverse event(s) that, in the judgment of the investigator, may cause severe or permanent harm or which rule out continuation of study drug
- General or specific changes in the patient's condition render the patient unable to receive further treatment in the judgment of the investigator
- Suspected pregnancy
- Serious non-compliance with the study protocol
- Lost to follow-up
- Patient withdraws consent
- Investigator removes the patient from study
- The Siteman Cancer Center decides to close the study

Patients who prematurely discontinue treatment for any reason will be followed as indicated in the study calendar. On infusion days, those patients who are not receiving study drug will still undergo pre and post-infusion assessments per PI and patient discretion. All subjects will be followed up to two years for the collection of survival data.

During the tolerability phase the study will continue for 6 cycles of mFOLFOX6. If the patient and the treating physician wish to continue lidocaine co-infusions with additional cycles of oxaliplatin, intravenous lidocaine can be prescribed at the discretion of the treating physician.

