6.11. Duration of Follow-up

In the tolerability phase, patients will have a follow-up visit prior to their 7th cycle of mFOLOFX6, and an additional visit at 8-10 weeks after 12th (or last, whichever is earlier) dose of oxaliplatin. In the randomized phase, patients will have a follow-up visit at 8-10 weeks after 12th (or last, whichever is earlier) dose of oxaliplatin. The main purpose of these visits is to compare the development of persistent neuropathy and neuropathic pain between the two study arms. Patients removed from study for unacceptable adverse events will be followed until resolution or stabilization of the adverse event. One year and again at two years after enrollment in the study, progression-free and overall survival will be assessed by review of the medical record.

7. **DOSE MODIFICATIONS**

In case of mild (Grade 1 AE) tachy- or brady- arrhythmias, or oxygen desaturation, the infusion will be paused, and attempted to resume 10 minutes after resolution of the adverse effect. In any case of moderate (Grade 2+) to severe tachy- or brady- arrhythmias (except sinus tachycardia, which is defined as DLT if Grade 3+), or oxygen desaturation, the infusion will be stopped, and patient withdrawn from the study.

In any case of serious side effects, the study team will follow the American Society of Regional Anesthesia (ASRA) guidelines on systemic local anesthetic toxicity [43]. Intralipid[®] infusion for possible local anesthetic systemic adverse effect management will be readily available and carried by the study the team.

The following stopping rules will be applied:

Lidocaine is not known to affect liver or kidney function. However, if the subject develops renal insufficiency (Creatinine clearance <30 ml/min) or liver insufficiency (ALT or AST >3 times upper normal value in patients with no liver metastases, ALT or AST >5 times upper normal value in patients with liver metastases) for any reason, the study drug will not be administered at that oxaliplatin treatment session for safety reasons. If prior to subsequent cycles of chemotherapy the limiting kidney/liver function improves beyond the above criteria, the study drug can be administered with oxaliplatin, within the same mFOLFOX6 regimen.

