10.1. Sample Size

To demonstrate a significant difference between Lidocaine and Placebo on oxaliplatin induced cold-allodynia after the first 8 cycles (intensity of pricking/tingling after 10 second contact will 8°C cylinder 7(\pm 2.2) in the placebo group vs. 4(\pm 2.2) in the lidocaine group [24]), with a two-sided t-test, assuming α =0.05 and 90% power (effect size 1.36), 26 evaluable subjects (13 per arm) will be required to participate in the study. We will enroll 30 evaluable subjects to the study due to potential drop-outs.

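### Sections 6.8 and 6.10 conflict on whether outcomes are still collected after withdrawal for neuropathy that needs drug treatment, and Section 10 has no rule for those patients' scores

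*Combined protocol and SAP*

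**What the plan says.** Section 6.8 says that adding a new drug for painful neuropathy "will not be allowed during the study", and continues: "Patients will be withdrawn from the study if the peripheral neuropathy is severe enough to require pharmacological treatment". Section 7 uses similar words for certain arrhythmia or desaturation events: "the infusion will be stopped, and patient withdrawn from the study".

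Section 6.10 lists the reasons for which treatment ends, among them "Investigator removes the patient from study", and then says: "Patients who prematurely discontinue treatment for any reason will be followed as indicated in the study calendar". On infusion days, however, "those patients who are not receiving study drug will still undergo pre and post-infusion assessments per PI and patient discretion". Section 6.11 has a separate sentence: "Patients removed from study for unacceptable adverse events will be followed until resolution or stabilization of the adverse event".

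The primary outcome (Section 9.1) is the cold-cylinder score after the first 8 mFOLFOX6 cycles, compared between arms. Section 10 adds daily home ratings through those cycles and up to a 2-week follow-up. Section 10.1 bases the sample size on a two-sided t-test and concludes that "26 evaluable subjects (13 per arm) will be required to participate in the study", with 30 enrolled to allow for drop-out. Sections 9.1, 10 and 10.1 name no efficacy analysis set, no rule for missing scores, and no handling of scores recorded after neuropathy medication starts.

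**The concern.** The trigger in 6.8 is the severity of the condition that the trial aims to prevent. If leaving the study also ends measurement, the missing scores are not a random sample: they tend to be the worst, and if lidocaine works most of them are in the placebo arm. Comparing only patients with a score would then shrink a real effect.

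At stake are the after-8-cycle cold score, the 8-10 week visit and any secondary outcome measured to last follow-up. Section 6.11 says that the main purpose of the follow-up visits is to compare persistent neuropathy and neuropathic pain between arms, and these patients carry much of that information. The Grade 2+ neuropathy outcomes are less exposed, because that grade would usually be recorded before the patient leaves.

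**Working it through.** **1. The plan's own figure.** Inputs from Section 10.1: means 7 and 4, SD 2.2, two-sided alpha 0.05, power 90%. Effect size = (7 - 4)/2.2 = 1.36. The two-sample t-test (noncentral t) needs 12.35 per arm, rounded up to 13, or 26 in total. Power is 91.5% at 13 per arm and 95.0% at 15 per arm. The sample size reproduces. The drop-out allowance is 30 - 26 = 4 patients (4/30 = 13.3%), with no rate or reason stated.

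**2. The passages side by side.**

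| Section | Event | What follows |
|---|---|---|
| 6.8 | Neuropathy needs drug treatment | Out of the study |
| 7 | Certain infusion events | Out of the study |
| 6.10 | Treatment stops, any reason | Calendar follow-up; infusion-day assessments discretionary |
| 6.11 | Removal for unacceptable adverse events | Followed until the event settles; outcome testing not mentioned |

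No passage says which row governs outcome collection for a patient withdrawn under 6.8.

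**3. Direction of the effect, by formula.** Suppose patients whose score exceeds a cut-off c are lost. The mean of those remaining is mu - 2.2 x phi(a)/Phi(a), with a = (c - mu)/2.2. Take c = 9.
- Placebo: a = (9 - 7)/2.2 = 0.909; 18.2% lost; remaining mean 6.29.
- Lidocaine: a = (9 - 4)/2.2 = 2.273; 1.2% lost; remaining mean 3.93.
- Observed difference: 6.29 - 3.93 = 2.36, against a true 3.0.

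**4. Size under assumed rates.** Simulation with 15 per arm. Score = arm mean + 2.2z, clipped to 0-10. Severity driving withdrawal = arm mean + 2.2(rho z + sqrt(1 - rho^2) e), with z and e independent standard normal. The withdrawal threshold is the same in both arms and is set to give the placebo rate shown. The rates and rho are assumptions, and the model lets lidocaine lower need for medication as much as it lowers the score. The analysis is a pooled t-test on patients with a score. Ranges run over rho = 1.0 to 0.3.

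| Placebo withdrawal | Lidocaine withdrawal | Observed difference | Power |
|---|---|---|---|
| 0% | 0% | 2.9 | 95% |
| 5% | 0.1% | 2.73-2.82 | 93-94% |
| 9% | 0.3% | 2.60-2.79 | 91-92% |
| 18% | 1.1% | 2.33-2.72 | 85-89% |
| 32% | 3.4% | 1.98-2.63 | 73-82% |

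- Clipping to the 0-10 scale alone takes the difference from 3.0 to 2.9.
- Power falls below 90% beyond about 10% placebo withdrawal at rho 1.0, 12% at 0.5 and 15% at 0.3.
- At rho = 0 there is no bias (difference 2.88-2.89); power at 18% is 92%, from lost numbers alone.
- With equal arm means, type I error is 4.7-5.2%.
- With a true 2-point effect, power is 67% without loss and 57-61%, 49-55% and 36-47% at 9%, 18% and 32%.

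**5. Selection versus numbers.** Exact power with 12 against 15 patients lost at random is 92.3%, so a few random losses do little. If the 30 evaluable subjects in 10.1 means that lost patients are replaced to 15 per arm, power is 92.4-93.5%, 89.3-92.7% and 83.9-91.0% at 9%, 18% and 32%, but the difference stays as shrunken as before.

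**6. Possible remedies, at 18% placebo withdrawal and a 3-point effect** (rho 1.0, 0.5, 0.3).

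| Handling | Difference | Power |
|---|---|---|
| Only patients with a score | 2.33, 2.61, 2.72 | 85%, 88%, 89% |
| All kept; medication lowers score by 1 | 2.72 at all three | 95%, 94%, 93% |
| All kept; lowers by 2 | 2.55 at all three | 94%, 91%, 89% |
| All kept; lowers by 3 | 2.38 at all three | 92%, 86%, 83% |

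A rank-sum test that gives triggered patients the worst rank keeps 93-96% power at all the rates run for a 3-point effect, but about 62-69% for a 2-point effect. Part of that comes from the assumption that lidocaine reduces need for medication.

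**The case against.** The strongest reply is that 6.10 already answers the question. A 6.8 withdrawal before cycle 8 is also an early stop of treatment, removal by the investigator is on the 6.10 list, and the next rule follows such patients per calendar. This stands as a fair reading, and it rules out saying that the plan makes no provision for them. It does not settle the matter, because 6.8 speaks of leaving the study rather than stopping study drug and neither section refers to the other.

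A reader might infer from 6.11 that follow-up of removed patients ends once the adverse event settles. The text does not say so: it sets a minimum for safety follow-up and is silent on outcome testing. Likewise, the bar on new medication during the study does not say that measurement stops.

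The discretionary infusion-day sentence also matters less for the primary score than it first appears. The calendar's randomised-phase treatment visits run from 1 to 8, with assessments before each infusion (Section 5). The after-8-cycle score may therefore come mainly from the home diary. The 8-10 week visit is tied to the last oxaliplatin dose, not to study drug.

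Finally, the trigger may be rare: oxaliplatin is reduced at persistent Grade 2 neuropathy (6.2) and as-needed analgesics are not limited (6.8). The documents give no rate, so this cannot be dismissed. None of these replies supplies an analysis set or a rule for post-medication scores.

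**Conclusion.** The point holds as an unresolved conflict between 6.8 (with 7) and 6.10, combined with a silent Section 10. It should be fixed before the data are analysed, with medium confidence in its practical weight.

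The understatement of benefit is conditional on five things: 6.8 is applied literally, only patients with a score are analysed, lidocaine works, it also reduces need for medication, and that need correlates with the cold score. The second is an inference, since the t-test appears only as the basis for the sample size. Under those conditions the loss is modest at 9% placebo withdrawal (difference about 2.6-2.8, power 91-92%) and material at 18-32% (about 2.0-2.7, power 73-89%), against 2.9 and 95%.

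Two stronger readings are not supported. The documents do not show that the worst-affected patients will be dropped from the analysis. Nor does the rule create a false-positive risk when the arms are equal. The exposure is a missed or shrunken effect in a pilot meant to show initial efficacy.

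**What to change.** Leave every clinical decision as it is.

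1. **Reconcile 6.8 and 7 with 6.10 and 6.11.** State that stopping study drug or starting neuropathy medication does not end outcome collection, and say whether the study in 6.8 means the study-drug period or all follow-up. Collect the after-8-cycle cold score (home cylinder and diary, or a visit) and the 8-10 week visit for every randomised patient unless the patient declines. If 8 cycles are not reached, fix a time for the score, such as about 16 weeks (8 x 14 days). Record the date on which neuropathy medication starts.
2. **Complete Section 10.** Analyse all randomised patients in their assigned arm and name one method for scores still missing. State in advance whether scores after medication are used as observed or handled otherwise; neither choice is best in every scenario above. Add a pre-specified rank-sum sensitivity analysis that gives neuropathy-related withdrawals or medication starts the worst rank.
3. **Report withdrawals by arm and reason.**

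The cost is wording in five sections (6.8, 6.10, 6.11, 7 and 10), a little extra follow-up and one extra analysis. There are three downsides. Scores after medication may be lower. A score taken off oxaliplatin may not compare well with one taken two weeks after a dose, because Section 1.3 ties cold hypersensitivity to the acute phase; this was not simulated. The worst-rank test answers a slightly different question from the mean difference, so it belongs only as a sensitivity analysis.

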6.9. Women of Childbearing Potential

Women of childbearing potential (defined as women with regular menses, women with amenorrhea, women with irregular cycles, women using a contraceptive method that precludes withdrawal bleeding, and women who have had a tubal ligation) are required to have a negative pregnancy test within 14 days prior to the first dose of lidocaine.

Female patients are required to use two forms of acceptable contraception, including one barrier method, during participation in the study.

If a patient is suspected to be pregnant, study treatment should be immediately discontinued. In addition a positive urine test must be confirmed by a serum pregnancy test. If it is confirmed that the patient is not pregnant, the patient may resume dosing.

6.10. Duration of Therapy

If at any time the constraints of this protocol are considered to be detrimental to the patient's health and/or the patient no longer wishes to continue protocol therapy, the protocol therapy should be discontinued and the reason(s) for discontinuation documented in the case report forms.

In the absence of treatment delays due to adverse events, treatment will continue for up to 6 cycles in the tolerability phase and 8 cycles in the randomized phase of mFOLFOX6 or until one of the following criteria applies:

- Documented and confirmed disease progression
- Death
- Adverse event(s) that, in the judgment of the investigator, may cause severe or permanent harm or which rule out continuation of study drug
- General or specific changes in the patient's condition render the patient unable to receive further treatment in the judgment of the investigator
- Suspected pregnancy
- Serious non-compliance with the study protocol
- Lost to follow-up
- Patient withdraws consent
- Investigator removes the patient from study
- The Siteman Cancer Center decides to close the study

Patients who prematurely discontinue treatment for any reason will be followed as indicated in the study calendar. On infusion days, those patients who are not receiving study drug will still undergo pre and post-infusion assessments per PI and patient discretion. All subjects will be followed up to two years for the collection of survival data.

During the tolerability phase the study will continue for 6 cycles of mFOLFOX6. If the patient and the treating physician wish to continue lidocaine co-infusions with additional cycles of oxaliplatin, intravenous lidocaine can be prescribed at the discretion of the treating physician.

6.11. Duration of Follow-up

In the tolerability phase, patients will have a follow-up visit prior to their 7th cycle of mFOLOFX6, and an additional visit at 8-10 weeks after 12th (or last, whichever is earlier) dose of oxaliplatin. In the randomized phase, patients will have a follow-up visit at 8-10 weeks after 12th (or last, whichever is earlier) dose of oxaliplatin. The main purpose of these visits is to compare the development of persistent neuropathy and neuropathic pain between the two study arms. Patients removed from study for unacceptable adverse events will be followed until resolution or stabilization of the adverse event. One year and again at two years after enrollment in the study, progression-free and overall survival will be assessed by review of the medical record.

7. **DOSE MODIFICATIONS**

In case of mild (Grade 1 AE) tachy- or brady- arrhythmias, or oxygen desaturation, the infusion will be paused, and attempted to resume 10 minutes after resolution of the adverse effect. In any case of moderate (Grade 2+) to severe tachy- or brady- arrhythmias (except sinus tachycardia, which is defined as DLT if Grade 3+), or oxygen desaturation, the infusion will be stopped, and patient withdrawn from the study.

In any case of serious side effects, the study team will follow the American Society of Regional Anesthesia (ASRA) guidelines on systemic local anesthetic toxicity [43]. Intralipid[®] infusion for possible local anesthetic systemic adverse effect management will be readily available and carried by the study the team.

The following stopping rules will be applied:

Lidocaine is not known to affect liver or kidney function. However, if the subject develops renal insufficiency (Creatinine clearance <30 ml/min) or liver insufficiency (ALT or AST >3 times upper normal value in patients with no liver metastases, ALT or AST >5 times upper normal value in patients with liver metastases) for any reason, the study drug will not be administered at that oxaliplatin treatment session for safety reasons. If prior to subsequent cycles of chemotherapy the limiting kidney/liver function improves beyond the above criteria, the study drug can be administered with oxaliplatin, within the same mFOLFOX6 regimen.

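### Section 7 can withdraw a patient for toxicity who has no DLT, so the tolerability rule can pass a dose despite such withdrawals, and the sections conflict on follow-up afterwards

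*Combined protocol and SAP*

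**What the plan says.** **Withdrawal.** Section 7 (Dose Modifications) pauses the infusion for Grade 1 events. It ends participation for "moderate (Grade 2+) to severe tachy- or brady- arrhythmias (except sinus tachycardia, which is defined as DLT if Grade 3" or higher), "or oxygen desaturation, the infusion will be stopped, and patient withdrawn from the study". Sinus tachycardia is the only exception.

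**DLT list.** Section 6.4.2 includes "Atrial Fibrillation Grade 3", "Atrial flutter, Grade 3" and "Atrioventricular (AV) block, Grade 3", each meaning that grade or higher. Paroxysmal atrial tachycardia, sinus bradycardia and ventricular arrhythmia are DLTs from Grade 2. Desaturation is not named. A catch-all covers any other event of Grade 3 or higher that is at least probably due to lidocaine.

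**Go rule.** Section 6.3 starts the randomised phase if the dose is "tolerable in four consecutive sessions of mFOLFOX6 in six or more of the eight patients". It then defines tolerability as the absence of DLTs and of unanticipated progression, and de-escalates when three or more patients have either. Objective 1 uses the same DLT-based definition. Section 6.4.3 proceeds with "Less than three of 8 subjects" having a DLT, and section 6.4.1 also counts DLTs alone.

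**Follow-up.** Section 6.10 states: "Patients who prematurely discontinue treatment for any reason will be followed as indicated in the study calendar". It leaves infusion-day assessments off study drug to the discretion of the investigator and the patient. Section 6.11 follows patients removed for unacceptable adverse events until the event resolves or stabilises.

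**The concern.** Exempting sinus tachycardia by reference to its DLT grade suggests that section 7 was meant to line up with section 6.4.2. The alignment is incomplete. Some patients taken off study for a toxicity will not enter the count that decides whether the dose is tolerable, and no section says how to classify or replace them. The synopsis asks for eight evaluable patients without tying that to four completed sessions. Section 6.5 makes anyone who received study treatment evaluable for toxicity.

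Two things are at stake. The first is Objective 1 and the dose carried into the randomised phase, which both depend on this count. The second is the primary outcome of that phase, cold-evoked stinging or pricking after 8 cycles. If lidocaine causes section 7 events and withdrawal ends data collection, the missing data would fall more in one arm. Section 10.1 needs 26 evaluable patients and enrols 30, a margin of 4. Section 10 names no analysis set and no rule for missing data.

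**Working it through.** **Step 1: compare the thresholds.** I read the Grade 2+ qualifier in section 7 as applying to desaturation too, because its Grade 1 sentence only pauses the infusion.

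| Event | Section 7 withdraws from | Section 6.4.2 DLT from | Withdrawn at Grade 2 without a DLT? |
|---|---|---|---|
| Atrial fibrillation | Grade 2 | Grade 3 | Yes |
| Atrial flutter | Grade 2 | Grade 3 | Yes |
| AV block | Grade 2, if a brady-arrhythmia | Grade 3 | Yes, on that condition |
| Paroxysmal atrial tachycardia | Grade 2 | Grade 2 | No |
| Sinus bradycardia | Grade 2 | Grade 2 | No |
| Ventricular arrhythmia | Grade 2 | Grade 2 | No |
| Sinus tachycardia | Exempt at Grade 2 | Grade 3 | No |
| Oxygen desaturation | Grade 2 | Catch-all only: Grade 3+, at least probably related | Yes |

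Leaving out the exempt sinus tachycardia, 3 of the 6 arrhythmias with a grade threshold are mismatched, and so is desaturation.

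**Step 2: reproduce the plan's rule.** Let d be the number of patients with a DLT (including unanticipated progression). If every failure is a DLT, section 6.3 proceeds when 8 − d ≥ 6 and section 6.4.3 when d < 3. Both mean d ≤ 2, so the stated thresholds agree exactly.

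**Step 3: add withdrawals without a DLT.** Let w be the number withdrawn under section 7, without a DLT, before completing four sessions. There are 9 + 8 + … + 1 = 45 pairs (d, w) with d + w ≤ 8.

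- *Definitional reading of section 6.3 (tolerable means no DLT).* Both sections proceed when d ≤ 2, whatever w is. They disagree in 0 of 45 pairs. With d = 0, the dose passes even at w = 8.
- *Strict reading (four sessions received and tolerated).* Section 6.3 needs d + w ≤ 2, while section 6.4.3 still needs only d ≤ 2. They differ when d ≤ 2 and d + w ≥ 3: six values of w for each of d = 0, 1 and 2, so 18 of 45 pairs. An example is d = 0, w = 3: 5 of 8 completed four tolerated sessions, with no DLT. In all 18 pairs section 6.4.3 says proceed. The go condition of section 6.3 is unmet, and so is its de-escalation trigger (three or more with DLT or progression), so section 6.3 gives no instruction. The reverse never occurs.

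In 15 of the 18 pairs, all but (1,2), (2,1) and (2,2), three or more patients were section 7 withdrawals.

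**Step 4: size, on assumed rates.** The documents give none. Assume independent patients, each with chance p of a DLT and chance q of a non-DLT withdrawal before completing four sessions. The chance of disagreement on the strict reading is

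P(d ≤ 2, d + w ≥ 3) = P(Bin(8, p) ≤ 2) − P(Bin(8, p + q) ≤ 2).

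For p = 0.10: 0.9^8 + 8(0.1)(0.9^7) + 28(0.01)(0.9^6) = 0.4305 + 0.3826 + 0.1488 = 0.9619. The other tails follow in the same way.

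| p | q | Section 6.4.3 proceeds | Section 6.3 proceeds (strict) | Difference |
|---|---|---|---|---|
| 5% | 2% | 0.9942 | 0.9853 | 0.9% |
| 5% | 5% | 0.9942 | 0.9619 | 3.2% |
| 10% | 10% | 0.9619 | 0.7969 | 16.5% |
| 15% | 15% | 0.8948 | 0.5518 | 34.3% |

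On the definitional reading the same difference is not a disagreement. It is the chance that the randomised phase starts although three or more of eight patients had a DLT or were withdrawn.

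**Step 5: follow-up.** Section 6.10 lists adverse events, and removal by the investigator, among the reasons for stopping treatment, and then keeps everyone who stops on the study calendar. Section 7 withdraws the patient from the study itself. Section 6.11 gives patients removed for adverse events an end point tied to the event. A Grade 2 arrhythmia falls under all three, and they do not give the same schedule.

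**The case against.** A reader might infer that sections 6.3 and 6.4.3 give opposite decisions on the same eight patients. The documents do not support that. Section 6.3 and Objective 1 both define tolerability by the absence of DLTs, and on that definition the sections always agree. Even on the strict reading, section 6.3 does not order de-escalation; it falls silent.

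A reader might also infer that such withdrawals will be frequent, or take 16% to 34% as the expected risk. Nothing in the documents supports this. Section 1.4 says that no study reported arrhythmias from intravenous lidocaine given for neuropathic pain, and section 3.2 excludes uncontrolled arrhythmias. Low rates are therefore plausible, and at those the figure is about 1% to 3%. Events in cycles 5 and 6 cannot affect the rule at all.

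It is also fair to say that stopping one patient and rejecting a dose level serve different purposes, so different thresholds are not in themselves an error. On follow-up, section 6.10 is broad, all subjects are followed for survival for up to two years, and section 6.11 can be read as adding to the calendar rather than replacing it. No figure supports a stated amount of data loss by arm.

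These points limit the size of the problem and do not remove it. The definition that makes the sections agree also allows a dose to pass with any number of section 7 withdrawals. The phrase about four consecutive sessions leaves the other reading open. A patient described as withdrawn from the study may reasonably be taken to have no further visits.

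**Conclusion.** The concern holds as an unresolved counting rule and an unreconciled follow-up rule. A patient can leave for a section 7 toxicity before completing four sessions and count as tolerating the dose, so the randomised phase could start with three or more of eight patients withdrawn in this way. On the strict reading of section 6.3, its go condition is unmet while section 6.4.3 says proceed, in 18 of 45 possible outcomes.

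The mismatch follows from the text alone, although including AV block depends on classing it as a brady-arrhythmia. The probabilities, from about 1% to 34%, rest on assumed rates, independent patients, the strict reading, and withdrawal before four sessions are complete. They show sensitivity and are not a forecast. The possible uneven loss of primary-outcome data depends on lidocaine causing the events and on withdrawal being read as the end of assessment; its size cannot be given from the documents.

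**What to change.** 1. Reconcile sections 6.3, 6.4.2, 6.4.3 and 7, and with them the DLT count in section 6.4.1. Give a patient withdrawn under section 7 before completing four sessions one stated classification, and use it in the same count of eight throughout. The choice of classification, and of any grade threshold, belongs to the clinical team. Once a single classification applies in either direction, all 45 outcomes give the same decision in both sections.
2. State what four consecutive sessions requires, and whether a patient withdrawn without a DLT is replaced.
3. Report section 7 withdrawals beside the DLT count when the tolerability result is presented.
4. Reconcile sections 7 and 6.11 with section 6.10, so that stopping study drug does not end collection of the primary outcome in the randomised phase for patients who still consent. This includes the wording that makes infusion-day assessments discretionary.

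The cost is protocol wording and continued collection of assessments already on the study calendar. No extra patients or new procedures are needed.
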